Protocol Title: Sound and Music for Mild Cognitive Impairment

NCT05064007

JHM IRB00295386

PI: [name]

[contact]

April 30, 2024

1. Abstract

Alzheimer's disease and related dementia (ADRD) seriously affect health and quality of life of 5.8 million older Americans. There are limited treatment options for AD and its associated progressive loss of cognition. One promising treatment possibility is auditory gamma stimulation, but much remains unknown. Emerging studies in humans found that 40 Hz sound induce neural gamma oscillation and enhanced cognitive function in older adults with and without AD. Our group has created 40 Hz music intervention by combining the selected music with 40 Hz sound and harmonizing the intensity (decibel) of 40Hz sound with the volume waveform of the selected music. This randomized controlled crossover study is to test the feasibility and preliminary efficacy of 4-week 40 Hz music intervention (A), 40 Hz sound (B) and preferred music (C) on cognitive function in 30 community-dwelling older adults with mild cognitive impairment (MCI). The participants will be randomized to three groups with different sequences of exposure to three conditions (Group 1 A-B-C; Group 2 B-C-A; Group 3. C-A-B). Participants will be instructed to listen to the assigned sequence of conditions, with each condition for one hour each day, five days a week for four weeks. There will be a 10-14 days wash-out break between each condition. Findings from this study will provide fundamental evidence for future development, selection, evaluation, and implementation of music/sound interventions for cognitive health in older adults with MCI.

2. Objectives

3.

Primary objective 1: Evaluate the feasibility of study and the three conditions: A (40 Hz music), B (preferred music), and C (preferred music 40Hz sound) in older adults with MCI.

Primary objective 2: Determine the preliminary efficacy of A for four weeks on cognitive function, compared with B and C.

4. Background

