This is a pilot feasibility study. We will use a randomized controlled crossover design to test the feasibility and preliminary efficacy of 40Hz music (Condition A) intervention, 40 Hz sound intervention (Condition B), and preferred music (Condition C) on cognitive function in 30 community-dwelling older adults with MCI. The participants will be randomized to three groups (n=10 in each group) with different sequences of exposure to three conditions. In each condition, participants will be instructed to listen to the assigned condition for one hour each day for 4 weeks. There will be a 10-14-day wash-out between each condition. Cognitive function, possible covariates including sleep, anxiety, depression will be collected at baseline and the end of each condition using validated measures. Qualitative semi-structured interviews will be conducted after completing each condition to understand participant's experience, preference, and acceptability of the three conditions. (Figure 1).

Recruitment: We aim to enroll 30 eligible older adults with MCI. The sample will be recruited from multiple sources including community recruitment, geriatric primary care and memory clinics affiliated with the Johns Hopkins University Health System, online recruitment. We will build upon successful recruitment strategies of the Johns Hopkins Center for Injury Research and Policy as well as the Center for Innovative Care in Aging which involves developing targeted study flyers, sending mailings by agencies and medical practices serving older adults, and working with community based advisory groups. The study flyers will be posted near the front desk and examine rooms of clinics, and the activity rooms in senior community centers; In addition, the study team will do presentations at the community center to inform residents of the research opportunity. Interested older adults will contact the research team or leave their contact information (name and phone number) and give

[figure not shown]

Figure 1: Proposed Study Procedure Chart

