oral permissions that the research team can reach them by phone or onsite. Interested older adults may be contacted on site or through a phone call by the research team. During initial contact with the older adults, the research assistant will describe the study, address any questions or concerns the participant may have. The research team will pre-screen interested older adults to determine eligibility (age, cognitive function, sedentary lifestyle, and poor sleep). If the participant verbally agrees to come in, the research team will schedule a meeting with the potential participant to complete the informed consent. Also, older adults who have participated in prior studies and expressed interest in being contacted for future research will also be invited to participate. In addition, we will be utilizing social media to promote recruitment efforts for this study. We will post the study flyer along with a Qualtrics survey on social media. We will be working collaboratively with the Institute for Clinical and Translational Research (ICTR) to have the study flyer posted on the ICTR JHU Studies Page. Network recruitment strategies will be used, and we will encourage participants to pass the study information on to family and friends. The research team will provide a participant referral incentive of \$25 for participants who refer others for enrollment in our research project.

Screening and Consent: Potential participants will first undergo a phone screening to elicit health history and receive detailed information about the study, then be scheduled for a meeting to complete writing consent, HIPAA authorization, and MCI diagnosis determination. A research personnel will meet with the potential participant at the research team office, clinic office or the participant's home per the participant's preference. During the meeting, we will start the consent process with the participant first. The research personnel will provide verbal and written description of the study in detail, allow the potential participant as much time as needed to read and ask questions, and then complete the informed consent. The consent form may be mailed or emailed to the participant before the meeting. After obtaining consent, we will assess participant's cognitive function to confirm the participant's eligibility for mild cognitive impairment using Montreal Cognitive Assessment, Activities of Daily Living, and Functional Activities Questionnaire (see details in Inclusion Criteria).

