Sample size and power: We will recruit 30-50 participants based on feasibility for recruitment and study cost estimation. With 10%-15% attrition, statistical power of 0.80, within-subject correlation (r) = 0.8, alpha of 0.05, we will be able to detect a moderate effect size (ES) of 0.5 for changes in cognitive outcomes overtime between conditions. If the ES turned out to be small, this study would provide precise ES for future efficacy trials.

Descriptive analysis will be performed to examine the underlying distributions of each outcomes measure. Distributional assumptions for the proposed statistical method will be verified and data transformation will be performed if required.

Aim 1 is to test the feasibility and acceptability of the three sound/music in older adults with MCI. Both qualitative and quantitative data will be used.

Qualitative data: we will code each transcript (naming segments of data with labels) and then use constant comparison (systematic comparisons of data with data, data with concepts, concepts with concepts, comparison within cases, and comparisons across cases). The interview guide may be revised if the findings suggest the need to include additional perspectives. We will file, index, and catalogue all data and use audit trails to trace the thinking and decision making by writing accurate and comprehensive notes and memos. Nvivo version 12 will be used to manage the interview data and field notes. Transcript of audio-recording with the filed notes will be analyzed using conventional content analysis to identify patterns, consistencies, and differences throughout the interviews.

Quantitative data: Descriptive analysis will be used to test recruitment, retention, adherence, and safety.

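### The sample-size paragraph promises a precise effect size if the effect is small, but its own inputs imply a 95% CI half-width of about 0.35; the 30-50 recruited is also not related to the 30 randomised

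*Combined protocol and SAP*

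**What the plan says.** Section 8 (Study Statistics, Sample size and power) opens with "We will recruit 30-50 participants based on feasibility for recruitment and study cost estimation". Its inputs are "With 10%-15% attrition, statistical power of 0.80, within-subject correlation (r) = 0.8, alpha of 0.05", from which it concludes "we will be able to detect a moderate effect size (ES) of 0.5 for changes in cognitive outcomes overtime between conditions". It then adds a fallback: "If the ES turned out to be small, this study would provide precise ES for future efficacy trials".

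The paragraph does not say which measurements the correlation of 0.8 links, which SD standardises the effect size, whether alpha is one- or two-sided, or what counts as small or precise. The Aim 2 text in the same section models post-minus-pre differences with a random intercept for participant.

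On numbers, the Abstract gives 30 participants. Section 5, Recruitment, says "We aim to enroll 30 eligible older adults with MCI", and the Overview of Study design says "The participants will be randomized to three groups (n=10 in each group) with different sequences of exposure to three conditions". The randomisation paragraph repeats 10 per group. Section 5, Screening and Consent, places consent before MCI is confirmed: "After obtaining consent, we will assess participant's cognitive function to confirm the participant's eligibility for mild cognitive impairment".

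**The concern.** A study sized to have 80% power at a moderate effect has, by construction, a standard error that is large relative to a small effect. Saying that a small effect would nevertheless be estimated precisely attributes to the design a property it does not have. The sentence matters because it is the value claimed for the pilot if the hoped-for effect does not appear. A later efficacy trial sized from such an estimate would rest on an interval that may run from no benefit to roughly the plan's own moderate effect.

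The sample size adds uncertainty. The paragraph with the precision claim works with 30-50, while every other section works with 30.

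**Working it through.** **Inputs.** From Section 8: power 0.80, effect size 0.5, r = 0.8, alpha 0.05, attrition 10%-15%, N = 30-50. From the Abstract and Section 5: N = 30, 10 per group. Completers, rounded down: 27/25 from N=30 and 45/42 from N=50. Assumed: two-sided alpha; 0.2 for a small effect, as the documents give no figure.

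**Step 1: what the power statement alone implies.** If 0.5 is detectable with exactly 80% power, SE = 0.5/(1.960 + 0.842) = 0.178, and the half-width is 1.960 x 0.178 = 0.35. This needs no view on r or on the SD unit, because the half-width is on the same scale as the 0.5.

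**Step 2: SD of the within-person contrast between two conditions' changes.** Four readings are possible:
- R1: r is between raw scores, effect in raw-score SD, changes independent across conditions. SD = sqrt(4(1 - 0.8)) = 0.894.
- R2: r is between change scores, effect in change-score SD. SD = sqrt(2(1 - 0.8)) = 0.632.
- R3: effect already in SDs of the paired difference. SD = 1.
- R4: effect in change-score SD, changes independent. SD = sqrt(2) = 1.414.

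**Step 3: reproduce the stated power** (paired t, noncentral t distribution, effect 0.5, N=30, 10%/15% attrition). R1: 0.798/0.765. R2: 0.977/0.966. R3: 0.706/0.670. R4: 0.424/0.396. R1 at 10% attrition reproduces 0.80. R3 needs 34 completers, so 34/0.90 = 37.8, rounded up to 38, or 34/0.85 = 40 recruited, which lies inside 30-50.

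**Step 4: expected half-width** = t(0.975, n-1) x SD / sqrt(n), with t = 2.056, 2.064, 2.015 and 2.020 for 27, 25, 45 and 42 completers. Example, R1 with 27: 2.056 x 0.894 / sqrt(27) = 0.354.

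| Reading (unit) | N=30, 10%/15% | N=50, 10%/15% |
|---|---|---|
| R1 (raw-score SD) | 0.354/0.369 | 0.269/0.279 |
| R2 (change-score SD) | 0.250/0.261 | 0.190/0.197 |
| R3 (paired-difference SD) | 0.396/0.413 | 0.300/0.312 |
| R4 (change-score SD) | 0.559/0.584 | 0.425/0.441 |

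Mixed-model degrees of freedom, 2(n-1), lower the N=30 values by 2-3%: at 10% attrition R1 becomes 0.345, R2 0.244, R3 0.386 and R4 0.546.

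**Step 5: set against a small effect of 0.2, N=30, 27 completers** (0.2 plus or minus the half-width).
- R1: -0.15 to 0.55; power 0.20.
- R2: -0.05 to 0.45; power 0.35.
- R3: -0.20 to 0.60; power 0.17.
- R4: -0.36 to 0.76; power 0.11.

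A half-width of 0.2 needs 80, 41, 99 or 195 completers on R1 to R4. For R2, the most favourable, that is 41/0.85 = 48.2, so 49 randomised at 15% attrition.

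**Step 6: the sample sizes.** Inflating 30 completers for attrition gives 30/0.90 = 33.3, so 34, and 30/0.85 = 35.3, so 36. Attrition therefore does not explain an upper figure of 50.

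**The case against.** The strongest defence is that the plan sets no precision standard, so none is breached. Comparing a half-width with the effect asks whether zero is excluded, which is a matter of significance. It is also a pilot whose size was set by feasibility and cost, and no analysis or decision rests on the sentence. Part of this stands: the 0.2 is an assumption, and an effect of 0.3 on R2 would just exclude zero (0.3 - 0.25 = 0.05, up to 0.55). But the claim fails as a statement about width too. An interval of 0.70 in total (twice 0.35) around a small effect is not precise in any sense useful for planning. The modest stakes bear on priority only.

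A second defence is that the paragraph says 30-50, and on R2, the reading closest to the Aim 2 random intercept on difference scores, N=50 reaches about 0.2. That is correct. But 30 is also in the range and is the figure used elsewhere, and R2 gives power of 0.97-0.98 at N=30, not 0.80.

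Several stronger inferences are tempting but not supported:
- *The 0.5 or the 80% power is wrong.* R1 reproduces it at N=30 with 10% attrition, R3 does so within 30-50, and R3 with one-sided alpha gives 0.81/0.78 at N=30.
- *R1 must be what was meant.* It falls to 0.765 at 15% attrition, and the match depends on two-sided alpha.
- *The half-width lies between 0.25 and 0.41.* Those values mix SD units, and R4 lies above them.
- *Every effect below 0.25 is smaller than its half-width at N=30.* On R2 the half-width is 0.244 with mixed-model degrees of freedom, or 0.236 with no attrition.
- *30-50 contradicts 30.* Recruiting 30-50 in order to randomise 30 is compatible with consent preceding confirmation of MCI. It is simply not written.

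**Conclusion.** The precision sentence is unsupported as written. The paragraph's own power statement implies a 95% half-width of about 0.35, assuming two-sided alpha 0.05. At N=30 with the stated attrition, explicit readings give 0.25/0.26 at best and 0.56/0.58 at worst, each in its own SD unit. For an assumed effect of 0.2, zero is inside the interval on every reading. Of the readings examined, only R2 reaches a half-width of about 0.2 at N=50.

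The sample-size mismatch is real but secondary: it is a missing explanation. Settling N alone would not settle the precision. At 15% attrition, going from 30 to 50 on R1 narrows the interval by 24% (0.279/0.369 = 0.76), whereas at N=30 the choice between R2 and R3 alone moves the stated figure from 0.261 to 0.413, a ratio of 1.58 (in different SD units).

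**What to change.** In Section 8, replace the precision sentence with the expected 95% CI half-width at the randomised N and 15% attrition, and say that effects will be reported as preliminary estimates with 95% CIs. In the same paragraph, state which measurements the correlation of 0.8 links, which SD the effect size uses and whether alpha is two-sided. If N is 30, the figure to insert is about 0.37 raw-score SD on R1, 0.26 change-score SD on R2, 0.41 paired-difference SD on R3 or 0.58 change-score SD on R4. The sponsor should choose the reading it intended and give one value.

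State one randomised N in the Abstract, Section 5 and Section 8. If 30-50 is the number to be consented before MCI is confirmed, say so beside it.

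This is low priority and changes wording only, with no added participants, procedures or analyses. The cost is that one stated claim becomes less favourable.

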Study randomization and blinding: Before enrollment, a randomization schedule in REDCap will be created using a random number generator. After baseline data collection, eligible participants will be randomized to three groups (n=10 in each group) with different sequences of exposure to three conditions. The study is a single-blind study. The data collector for outcome assessments will be blinded for participant's exposed condition.

Study duration: The total duration of the study participation will be around 18-20 weeks including 4 weeks of each condition, 10-14 days washout, and 1 week of data collection.

Number of study visits: There will be six data collection visits at the participant's home or at the School of Nursing based on the participant's preference. The 3 baseline data collections will take about 40 minutes. The 3 posttest data collections will take about 60 minutes.

Delivery of Music/Sound Interventions. Within 1 week of baseline data collection, participants will start their assigned sequence of study activity at their home. Participants will listen to the three music/sound conditions: A (40Hz music), B (Preferred Music), and C (40 Hz Sound) with their group assigned sequence (Group 1 A-B-C; Group 2 B-C-A; Group 3. C-A-B). The research team will provide a MP3 player and headphones for each participant to listen to the assigned music/sound during the study. The research team will set up the "listening station" at home with the participant before any assigned activity. Participants will sit on a comfortable chair in front of a table while listening to music/sound. The speaker will be placed on the table. Participants can move hands, stretch arms at the sitting or standing position or they can move around the table

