and then sit down if they feel sleepy during the session. The volume of sound/music will be adjusted to the participant's comfortable level, which will be used throughout the assigned listening condition (around 67-80 dB). Participants can listen to sound/music anytime between morning and at least 3 hours before bedtime. Mid-morning (9am-12pm) is the recommended time for the session as the tendency for sleep increases during the afternoon. In each condition, participants will be instructed to listen to the assigned condition for an hour 5 days a week for 4 weeks. The music interventionist or a research assistant will be present for the first two sessions of each condition to assist the participant set up the speaker and adjust volume etc. There will be a 10-14-day wash-out break between each condition. The sound/music list and the volume of sound/music will be updated based on the participant's exposed condition.

Condition A. personalized 40 Hz music: The 40Hz music playlist (15 to 20 pieces of 40Hz music) for each participant will be created using the same list of personal preferred music (See detail in C. Preferred music). The 40 Hz music pieces will be generated by mixing selected music and 40 Hz sound using Adobe Audition (Build 14.2.0.34). The volume of the 40Hz soundtrack will be adjusted to match the decibel level of the music playback. The harmonization of volume between 40Hz sound and the music playback is to make 40 Hz sound audible when the music is loud and improve musicality and avoid abruptness of 40 Hz when the volume of music is low. The music interventionist will assist the 40 Hz music creation.

Condition B. 40 Hz sound: The 40Hz soundtrack is generated using Adobe Audition (Build 14.2.0.34) and consists of a sound clip and a silent interval. In generating the sound clip, the base frequency is set to 17000Hz with a modulation depth of 7000Hz and the modulation rate is set to 40Hz per second. The decibel amplitude is -10.3 dB, and the duration is 1millisecond (ms). The duration of the silent segment is 25 ms. The sound clip and the silent interval are mixed down to a single piece of 25 ms and then repeat 40 times per second.

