Condition C. Preferred music: A personalized preferred music playlist with 15-20 pieces of music will be created. We ask the participant to complete the "Assessment of Personal Music Preference"⁴⁷, provide the names of their favorite music, and select preferred music pieces from our music library during baseline data collection. To maximize participant's enjoyment and potential musical effect, a personal playlist for each participant will be created using their identified/selected music pieces and individual genre of music by the music interventionist. The study music library will be expanded as we add more participant-suggested music.

Data collection: Data will be collected before and after each condition. In total, the study includes 3 baseline and 3 posttest data collections. Data collection will take place at the participant's home or in a private room at the School of Nursing, a private room at Wald Community Nursing Center, or JHU clinical research unit per the participant's preference. Demographic and other information, and music preference will be collected at 1st baseline data collection. Cognitive function, sweat neurology biomarkers, survey on sleep, anxiety, depression data will be collected at each baseline and posttest data collection. Semi-structured interview data will be collected at each posttest data collection. The interview conversations will be audio recorded and field notes will be taken by a research team member during the interview. We estimate each interview will last about 20 minutes. The participant will be asked to answer open-ended questions about the participant's experience with the study interventions. The voice recordings will be sent to Production Transcripts for transcription (<https://www.productiontranscripts.com/>).

Measures:

Primary outcome 1: Episodic Memory will be measured using "One Card Learning" (visual)and International Shopping List, and Delayed Recall"(verbal) using Cogstate Alzheimer's Battery

(CAB). A composite episodic memory score will be calculated by taking the average of the standardized scores across the three tests

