Aim 2 is to determine the preliminary efficacy of A for four weeks on cognitive function, compared with B and C. Linear mixed effect (LME) models will be used to examine the change in the outcome measures over time, with the post-pre difference score as the dependent variable. LME models allow the analysis of unbalanced data. The data is considered unbalanced when the study participants have varied number of observations and the observation times differ among the study participants. The model includes condition (treatment) as a fixed effect of primary interest, and controlled for sequence (as a fixed effect) to account for potential order effects due to the crossover design. Age and sex will be included as additional covariates. A random intercept for participant is specified to account for within-subject correlation across conditions.

Treatment of Missing Data. With the use of direct data entry, we expect to minimize missing data. We will obtain reasons for the study drop-outs so that we can assess the missing data mechanism. The pattern of missingness will be examined, and baseline responses compared between those with and without missing data. Variables related to missingness will be included in the analyses, which should yield valid inferences. We will use imputation to impute missing data

and then compare the results from with and without imputation. If the assumption of missing at random is reasonable, likelihood-based methods that ignore the response mechanism will be appropriate. If the probability of missingness depends on the unobserved data even after the observed data are conditioned (i.e., non-ignorable missingness), we will consider both selection models and pattern-mixture models to guide our chosen model. The effect of our assumptions on inferences regarding the missing mechanism will be assessed using sensitivity analyses.

9. Risks

Minimal risks to study participants are expected. Subjects may experience boredom or feel the sound/music is unpleasant during the sessions. The risk is minimized as we use participant preferred music and 40 Hz music to develop the personal playlist. We will stop the assigned sound/music exposure if the participant reports that they feel uncomfortable or cannot tolerate the condition. In addition, the participant may experience psychological reactions to completing the questionnaire data and cognitive tests. Since the questions are benign, the risk is minimal.

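### Aim 2 uses the period baselines only by subtraction; adding them as covariates, with a period term, would tighten A−B and A−C at no data cost if the washout is adequate

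*Combined protocol and SAP*

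**What the plan says.** Section 8, Aim 2, specifies a linear mixed model "with the post-pre difference score as the dependent variable". Its fixed effects are condition and sequence, and it has a random intercept for participant. On further terms it says only: "Age and sex will be included as additional covariates". No baseline cognitive score and no period effect is listed.

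Section 5, Data collection, provides three baselines and three post-tests per participant: "Cognitive function, sweat neurology biomarkers, survey on sleep, anxiety, depression data will be collected at each baseline and posttest data collection". The sequences are cyclic ("Group 1 A-B-C; Group 2 B-C-A; Group 3. C-A-B"), and on washout Section 5 says: "There will be a 10-14-day wash-out break between each condition".

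The sample-size paragraph in Section 8 gives a single correlation, "within-subject correlation (r) = 0.8", without saying which visits it links. It claims power of 0.80 for an effect size of 0.5 at alpha 0.05 with 10%–15% attrition. On numbers and purpose it says: "We will recruit 30-50 participants based on feasibility for recruitment and study cost estimation" and "If the ES turned out to be small, this study would provide precise ES for future efficacy trials".

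**The concern.** A change score is a baseline adjustment with the slope set to 1 in advance. In a crossover, the slope that matters for A−B and A−C is the within-participant one: how far a participant's baseline in one period, relative to their own average, predicts the post-test in that period. If visits are about equally correlated, that slope is near 0, and subtracting the baseline adds its noise to the outcome. The baselines needed to estimate the slope are already collected.

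What is at stake is precision, not validity. It matters most near 30 enrolled, where planned power is only just 0.80. It also bears on the stated wish for a precise effect size if the effect proves small.

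**Working it through.** **Inputs.** From Section 8: r = 0.8, alpha 0.05 (two-sided assumed), effect size 0.5 (assumed in SD units of the score), 30–50 recruited, 10%–15% attrition. Not in the documents: the cross-period correlation, called rb here and varied from 0.8 to 0.5. The same-period pre-post correlation, rw, is taken as 0.8.

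**1. The plan's own figure.** With unit score variance, the difference of two change scores within a participant has variance 4(1 − rw) = 4 × 0.2 = 0.80. Completers needed: (1.96 + 0.84)² × 0.80 / 0.5² ≈ 25.1, so 26. Inflated for attrition, 26/0.90 = 28.9 and 26/0.85 = 30.6, which brackets 30. By noncentral paired t, 27 completers (30 × 0.90) give power 0.80. The stated power is reproduced on this reading.

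**2. Variance with an estimated slope.** Differences between two periods in post-test and in baseline each have variance 2(1 − rb), and their covariance is 2(rw − rb). The best slope is ρ = (rw − rb)/(1 − rb). Then:
- change score: 4(1 − rw) = 4(1 − rb)(1 − ρ)
- adjusted: 2(1 − rb)(1 − ρ²)
- ratio: 2/(1 + ρ)

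**3. Results at rw = 0.8, 27 completers** (change score: variance 0.80, power 0.80, detectable effect 0.50 SD, 95% CI half-width 0.35).

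| rb (assumed) | ρ | Adjusted variance | Ratio | Power for 0.5 SD | Detectable effect (SD) | Half-width |
|---|---|---|---|---|---|---|
| 0.80 | 0.00 | 0.40 | 2.00 | 0.98 | 0.35 | 0.25 |
| 0.75 | 0.20 | 0.48 | 1.67 | 0.95 | 0.39 | 0.27 |
| 0.70 | 0.33 | 0.53 | 1.50 | 0.93 | 0.41 | 0.29 |
| 0.60 | 0.50 | 0.60 | 1.33 | 0.90 | 0.43 | 0.31 |
| 0.50 | 0.60 | 0.64 | 1.25 | 0.88 | 0.45 | 0.32 |

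At 50 enrolled (42–45 completers), change-score power is already 0.94–0.96, against 0.98–0.999 adjusted. Half-width at 45 completers is 0.27 against 0.19–0.24.

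**4. Check by simulation.** Random-intercept model, the three cyclic sequences, 27 completers, 1,500 runs, no carryover. At rb = 0.8/0.7/0.6/0.5 the empirical SE of A−B was 0.169/0.169/0.174/0.170 for the plan. It was 0.118/0.140/0.154/0.154 with both baseline terms and period. Squared ratios: 2.05/1.46/1.28/1.22. Rejection rates were 0.81–0.84 for the plan and 0.98/0.94/0.89/0.90 adjusted. Both were essentially unbiased. Type I error at rb = 0.7 was 0.049 and 0.056.

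**5. Which baseline terms.** A single pooled baseline covariate gave ratios of only 1.19–1.34, because one slope must serve between- and within-participant relations. The first baseline alone gave 1.00.

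**6. Why a period term.** Six repeated tests can produce practice gains, which pull the within-participant slope towards 1. Without a period term, at correlations of 0.8, assumed gains of 0.2–0.3 SD per visit cut the ratio from about 2.0 to about 1.66–1.40.

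**7. Carryover.** In two of the three sequences B follows A; in the third B comes first. Suppose A's effect is 0.5 SD, B's is 0, half of A's effect remains at the next baseline, and all correlations are 0.8 (all assumed). B's average baseline is then raised by 2/3 × 0.25 = 0.167.

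| Carryover of 50% | Change score, true A−B 0.50 | Adjusted, true A−B 0.50 | False rejection if A = B: change / adjusted |
|---|---|---|---|
| persists to post-test | 0.50 | 0.33 (coverage 0.75) | 0.05 / 0.26 |
| fades before post-test | 0.67 (coverage 0.84) | 0.50 | 0.16 / 0.05 |

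**8. The gap between models.** With no carryover and rb = 0.8, its variance at 27 completers is (0.80 − 0.40)/27 = 0.0148, an SD of 0.12. By simulation it exceeds 0.10 in 40% of trials. Under 50% carryover its expected value is +0.17 in both rows of the table above (0.50 − 0.33 and 0.67 − 0.50).

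**The case against.** The strongest reply is that the choice lies between two legitimate models in a pilot feasibility study whose efficacy aim is preliminary. The planned contrast is unbiased without carryover and roughly delivers its stated power, so nothing is broken. That stands, and it limits this to an optional improvement.

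Second, the size of the gain is not in the documents. One might infer from r = 0.8 that the plan simply doubles the variance. The text does not support that, because it does not say 0.8 applies across periods. Nor are 1.25 and 2.0 fixed bounds: rw = 0.9 with rb = 0.5 gives 1.11, and rw = 0.75 with rb = 0.80 gives 2.67. The direction is firmer. For any ρ below 1 the ratio exceeds 1, apart from the small cost of estimating slopes and provided there is no carryover.

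Third, baselines 2 and 3 follow earlier conditions, and each condition always has the same predecessor, so adjustment gives up some robustness. This is a real cost, and in the example the worst false-rejection rate is higher for the adjusted model (26% against 16%). But the change score is not generally protected either; it fails when carryover fades before the post-test.

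Finally, Section 8 would compare baseline responses by missingness and add variables related to missingness. That is a missing-data provision, not a planned adjustment for baseline score.

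**Conclusion.** The point holds as a low-cost efficiency gain. At rw = 0.8 and an assumed rb of 0.8 to 0.5, the planned variance of A−B and A−C is about 2.0 to 1.25 times what the collected data allow. That is an SE reduction of 29% to 11% (1 − √0.50 to 1 − √0.80). The power gain matters near 30 enrolled and is small near 50; intervals narrow by the same proportion at any size.

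This rests on the effect size being in score-SD units, equal cross-period correlations and an adequate washout. Neither model dominates under carryover.

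A reader might infer that the planned analysis is invalid or underpowered; the plan's own inputs do not support that. A reader might also treat disagreement between the two models as evidence of carryover. It is not usable that way: the gap is often large by chance at this sample size, and it cannot tell persistent from faded carryover, for which opposite models are right.

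**What to change.** In Section 8, Aim 2, keep the mixed model and the change score as dependent variable. Add three items:
- a fixed effect for period;
- the participant's mean of the available period baselines;
- each period baseline's deviation from that mean.

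The outcome need not be switched to the post-test score. The baseline is the sum of the two added terms, so both outcomes give identical condition contrasts. Name the planned unadjusted change-score model as a sensitivity analysis, and say in advance that each model is biased under a different carryover pattern. Do not pre-state that a gap between them indicates carryover.

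The cost is analysis wording, two slopes and a period factor; no new data or visits. Participants who drop out will have a mean based on fewer baselines. The main price is the adjusted model's exposure to carryover that lasts to the next post-test.
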